11. MEASUREMENT OF EFFECT

11.1 Antitumor Effects and Endpoints

Although response is not the primary endpoint of this trial, patients with measurable disease will be assessed by standard criteria. For the purposes of this study, patients should be re-evaluated at follow-up visits within one month of completion of radiotherapy, and then subsequently every 3 months for one year. CT of the chest, abdomen, and pelvis, and any other pertinent imaging (e.g. CT or MRI head for brain metastases) are required within 28 days of each follow-up visit.

Response and progression will be evaluated in this study using the international criteria proposed by the Response Evaluation Criteria in Solid Tumors (RECIST) Committee [68]. Changes in only the largest diameter (unidimensional measurement) of the tumor lesions are used in the RECIST criteria.

11.1.1 Definitions

Evaluable for toxicity. All patients will be evaluable for toxicity from the time of their first treatment with radiotherapy.

Evaluable for objective response. Patients who have had their disease re-evaluated following completion of radiotherapy will be considered evaluable for response. These patients will have their response classified according to the definitions stated below.

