5. TREATMENT PLAN

5.1 Study Design

This is a pilot study of the use of SBRT to all sites of disease for patients with oligometastatic RCC. Patients may receive off-protocol systemic therapy per medical oncologist discretion no earlier than 4 weeks after starting SBRT. While there are no restrictions on systemic therapy following SBRT, caution is advised on the use of bevacizumab given prior case reports demonstrating the possibility of heightened toxicity when this agent is used in the setting of SBRT. Limited or symptomatic recurrences can also be treated with radiation therapy (either SBRT or conventional therapy) at the clinician's discretion.

Enrollment will proceed according to a sequential toxicity monitoring schema to test the null hypothesis of a $\pi_0=5\%$ grade 4 toxicity rate against an upper acceptable boundary of a $\pi_1=20\%$ grade 4 toxicity rate. Trial enrollment will be halted if there are two grade 4 events within the first 2 patients, if there are three events within the first 14 patients, or if there are four events within the first 25 patients. The treatment will be considered successful if there are less than four events in 25 evaluable patients (<16%).

Treatment will be administered on an outpatient basis. The details of planning and administration of radiotherapy are discussed in detail in section 6. Reported adverse events and potential risks for SBRT are described in Section 8. Appropriate dose modifications for SBRT are described in Section 6. No investigational or commercial agents or therapies other than those described below may be administered with the intent to treat the patient's malignancy.

The pilot study will be considered successful if 25 patients are accrued, with less than 4 having Grade 4+ toxicity events after SBRT.

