5.2 Definition of Grade ≥ 4 RT-related Toxicity

The evaluation period of acute toxicity will be defined by the period of 90 days following the first fraction of RT. Of note, late grade ≥ 4 toxicity occurring beyond 90 days and through the one year of planned post-treatment follow-up will still have the ability to modify the trial design and accrual per the discretion of the primary investigator. Grade ≥ 4 toxicity will be defined

according to Common Toxicity Criteria version 4.0 (ctep.cancer.gov/reporting/ctc.html). Toxicities will be classified by a study committee as likely due to SBRT or non-radiotherapy-related based on review of nature of toxicity and the areas being treated with radiotherapy.

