5.6 Criteria for Removal from Study

Patients will be removed from study when one of the following criteria applies:

- Intercurrent illness that prevents administration of SBRT,
- Unacceptable adverse event(s),
- Death,
- Patient decides to withdraw from the study, or
- General or specific changes in the patient's condition render the patient unacceptable for further treatment in the judgment of the investigator/treating physician.

The reason for study removal and the date the patient was removed must be documented in the Case Report Form.

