12. STATISTICAL CONSIDERATIONS

12.1 Study Design/Endpoints

This is a pilot study of the use of 5-fraction SBRT for oligometastatic RCC. Patients enrolled in the study will be treated with SBRT to all sites of disease. Enrollment will proceed according to a sequential toxicity monitoring schema [69] to test the null hypothesis of a $\pi_0=5\%$ grade 4 toxicity rate against an upper acceptable boundary of a $\pi_1=20\%$ grade 4 toxicity rate. Trial enrollment will be halted if there are two grade 4 events within the first 2 patients, if there are three events within the first 14 patients, or if there are four events within the first 25 patients. The treatment will be considered successful if there are less than four events in 25 patients, i.e., $<16\%$ observed toxicities. This design has approximately 80% power (78.8%) to declare the treatment too toxic if the true grade 4 toxicity rate is $\pi_1=20\%$.

Patients will be followed for a total of one year after completion of the trial per protocol. Patients may be treated with off-protocol systemic therapy no earlier than 2 weeks after completion of RT. The primary endpoint is the rate of grade 4 RT-related toxicity with this treatment approach. Secondary endpoints include determining the toxicity profile of 5-fraction SBRT, determining the feasibility of 5-fraction SBRT based on normal tissue dosimetric constraints based on the organ site of involvement, describing the LeC, PFS, and patterns of failure of this approach, as well as to explore the feasibility of accrual and the adequacy of the eligibility criteria of this approach.

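### One fraction makes a patient evaluable for toxicity, so event-free early leavers fill places in the fewer-than-4-of-25 success count as non-events and tilt it modestly toward declaring safety

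*Combined protocol and SAP*

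**What the plan says.** - **Who is evaluable.** Section 11.1.1: "All patients will be evaluable for toxicity from the time of their first treatment with radiotherapy". It sets no minimum number of fractions and no minimum follow-up. The same section makes a patient evaluable for response only after disease has been re-evaluated following radiotherapy, so a post-treatment condition exists for response but not for the primary endpoint.
- **How success is decided.** Section 5.1: "The treatment will be considered successful if there are less than four events in 25 evaluable patients (<16" percent). Section 12.1 repeats the rule without the word evaluable, and section 12.2 caps the sample at 25 evaluable patients. Neither has a replacement rule or a dropout allowance.
- **Halting boundary.** Section 12.1: "Trial enrollment will be halted if there are two grade 4 events within the first 2 patients". Its two later limits are a third event by patient 14 and a fourth by patient 25. The hypotheses are a 5% rate against a 20% rate.
- **Power.** "This design has approximately 80% power (78.8%) to declare the treatment too toxic if the true grade 4 toxicity rate is" 20%.
- **Time window.** Section 5.2: "The evaluation period of acute toxicity will be defined by the period of 90 days following the first fraction of RT". Later grade 4 or higher events, up to one year, may change the trial at the investigator's discretion.
- **Ways to leave.** Section 5.6 lists "Intercurrent illness that prevents administration of SBRT", unacceptable adverse events, death, withdrawal and deterioration.
- **Follow-up.** Section 5.5 plans one year for all patients. After removal it promises continued follow-up explicitly only for unacceptable adverse events.
- **Reported estimate.** The synopsis (analytic plan for the primary objective) adds a Kaplan-Meier estimate of freedom from grade 4 or higher RT-related toxicity.

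**The concern.** The success rule is a count over a fixed number of places. A treated patient with no recorded event adds one to the denominator and nothing to the numerator, whether observed for a year or for three weeks. The primary objective concerns delivery of the SBRT course to all sites. A patient who stopped after one fraction, or was not seen to day 90, says little about whether that course causes severe toxicity. For event-free patients the error runs one way: each such place makes it easier to stay below four events.

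At stake is the reliability of the decision. The synopsis says the results will feed a larger phase II study. The design starts just under 80% power to flag a 20% toxicity rate, so it has little room to lose any.

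**Working it through.** **Inputs.** Boundary 2 of 2, 3 of 14, 4 of 25, rates 5% and 20%, and stated power 78.8% are from 12.1. The exit rate *d* is not in the documents, so I assume 5% and 10% and show the range. The share *u* of an early leaver's event risk that goes unseen is also assumed: 1 (all) or 0.5 (half). The synopsis study-design text carries a different halting rule (3 of the first 10); that is a separate inconsistency and is not used here.

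**Step 1: reproduce the plan's figure.** Let S(n,k) be the probability of *k* events after *n* patients without having halted. Then S(n,k) = (1−p)·S(n−1,k) + p·S(n−1,k−1). Probability moves to halted when *k* reaches 2 by n=2, 3 by n=14 or 4 by n=25.
- p = 0.20: 0.7884, matching the stated 78.8%.
- p = 0.05: 0.0500, the type I error.

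Both assume every patient's event status is fully observed.

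**Step 2: early leavers counted as non-events.** The rate that the count can see is p(1 − d·u). Put into the same recursion:

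| Exit *d* | Unseen share *u* | Visible rate at p = 0.20 | Power | Type I error |
|---|---|---|---|---|
| 5% | 0.5 | 0.195 | 77.1% | 4.7% |
| 5% | 1 | 0.190 | 75.2% | 4.3% |
| 10% | 0.5 | 0.190 | 75.2% | 4.3% |
| 10% | 1 | 0.180 | 71.1% | 3.7% |

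Both error rates move toward declaring success.

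**Step 3: a scale for *d* from the documents.** Section 2.3 quotes overall survival of 32 months in a phase II SBRT study of RCC. Read as a median under an exponential model, deaths by three months are 1 − 0.5^(3/32) = 6%. At d = 6% the visible rate is 0.188 (u = 1) or 0.194 (u = 0.5), giving power of 74.4% or 76.7%. That is a loss of about 4 or 2 points. Withdrawals would add to *d*; deaths after a recorded event would not.

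**Step 4: what refilling does.** Suppose leavers with an event are kept and event-free leavers are replaced. With *h* = 1 − u the share of leavers' risk that is seen, the rate among evaluable patients is p(1 − d + dh) / (1 − d + dhp). At p = 0.05 and d = 10%:
- h = 0.5: 0.0475/0.9025 = 0.0526, type I error 5.7%.
- h = 1: 0.0500/0.9050 = 0.0552, type I error 6.5%.

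These apply all three steps to evaluable patients. If the 2-of-2 and 3-of-14 steps stay on treated patients and only the final step runs to the 25th evaluable patient, each patient has three outcomes: event, p(1−d+dh); evaluable event-free, (1−d)(1−p); not evaluable, d(1−hp). The recursion then gives 5.3% and 6.1%. Expected enrolment at 10% exit is about 25/0.9 = 28.

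**Step 5: without refilling.** Stopping the step 1 recursion at fewer fully observed patients, with the four-event limit kept, gives power at 20% of 76.4% for 24, 73.8% for 23 and 71.1% for 22.

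**The case against.** The strongest reply has five parts.

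- **Nothing in the documents says early leavers are scored as toxicity-free.** True; their handling is unstated. A raw count over 25 places has that effect by default for anyone without a recorded event.
- **Stopping SBRT is not leaving observation.** This stands in large part. Section 5.5 plans a year of follow-up, the study calendar schedules adverse-event checks throughout, and radiotherapy is due to finish by day 28, so many early leavers would have had the full course. Patients with a grade 4 or higher RT-related event count as events whenever they stop. Part of the 5.6 item on illness concerns patients never treated, whom 11.1.1 already leaves out.
- **Kaplan-Meier deals with censoring.** It does so for the reported estimate, not for the success decision.
- **All treated patients is the usual safety set.** Agreed. Simply dropping early stoppers would be worse: if, as an illustration, 10% stop early and carry 30% of events, the rate among the rest is 0.20 × 0.70/0.90 = 0.156 and power falls to 59.4%. Any remedy must keep every event.
- **If 20% means the rate among all treated patients, 78.8% stands.** Correct. The loss arises only if 20% is the rate for a fully delivered and observed course.

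A reader might also infer a large loss by applying the 6-15 month median survival in the background, which gives 13-29% deaths by three months. The documents do not support that. The figure describes metastatic RCC in general, the synopsis sets oligometastatic patients apart from it, and eligibility requires ECOG 0-2 and a life expectancy of at least 3 months.

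**Conclusion.** The gap is real and modest. Sections 11.1.1, 5.1 and 12.1 together let an event-free patient with partial treatment or short observation fill a place as a non-event, and no other provision corrects the count. The direction is toward success. The size rests on an exit rate the documents do not give: about 2 to 4 points of power at 5% exit and about 4 to 8 points at 10%, according to how much of the leavers' risk goes unseen.

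A reader might infer that 78.8% is wrong, or that true power is near 60%. Neither follows. The 78.8% is exact for 25 fully observed patients. A fall to 61.7% needs 20% of patients to be wholly uninformative (visible rate 0.20 × 0.80 = 0.16), and nothing in the documents points to that. The plan should settle the rule before the success criterion is applied.

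**What to change.** 1. In 11.1.1, keep all treated patients for the halting boundary and the safety tables.
2. For the success rule, define a patient as evaluable if they had a grade 4 or higher RT-related event at any time after the first fraction, or completed the planned SBRT and were observed event-free through the 90-day window of 5.2. Naming the window matters, because 5.2 describes both 90 days and one year.
3. Report the number not evaluable, with reasons.
4. Choose one of two routes in 12.1 and 12.2. Either refill those places up to the 25 evaluable patients that 12.2 already names, and say that the four-event limit runs until the 25th evaluable patient. Or do not refill, state that 78.8% assumes full observation, and give the power for the number actually evaluable.

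**Cost.** A few sentences in 11.1.1, 12.1 and 12.2. Refilling means a few more patients (about 28 treated at 10% exit, so the enrolment figure of 25 in the schema would need to agree). It also brings a small rise in type I error, from 5.0% to about 5.7-6.5% at 10% exit, because event-free leavers are replaced while those with events are kept. That error is on the cautious side. Not refilling means a less favourable stated power.

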2.4.1 Rationale for Secondary Objectives

Patients with sites of metastatic disease commonly present with pain from these lesions. Conventional radiotherapy can offer palliation for most patients, but the durability of pain control is variable. In order to describe the clinical efficacy of this treatment approach, we will also evaluate objective response rate, treated lesion control, and the patterns of failure.

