12.2 Sample Size/Accrual Rate

The maximum sample size will be 25 evaluable patients according to the schema above. This sample size is needed in order to signify feasibility of this disease approach and accrual to a larger, later phase trial.

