12.5 Analysis of Secondary Endpoints

The secondary endpoints of this study include determining the toxicity profile, LeC, and patterns of failure of this approach, as well as the feasibility of a 5-fraction SBRT regimen based on normal tissue dose constraint and treatment goals, and the feasibility of accrual to an oligometastasis trial in RCC and adequacy of the eligibility criteria.

A database will be created that is HIPAA compliant to store the information to perform analyses. A unique study number will be assigned to each patient that will be used for all analyses. Variables will be defined as described in section 11. The results of analyses will be described but no formal statistical analysis will be performed.

Grade ≥ 4 RT-related toxicities will be recorded in database and are described as in section 5.2. The ultimate allocation of a toxicity as RT-related or non-RT-related will be decided by the study committee. Toxicities of interest that occur within the 3-12 month time frame after RT start will be documented and analyzed using descriptive statistics.

The durations of treated lesion control, organ-specific control, distant metastasis free survival, progression-free, overall and cause specific survival as defined in section 11.1.5 will be calculated for each patient. Descriptive statistics will be used to estimate these secondary endpoints using the Kaplan-Meier method (secondary aims 1.2.1, 1.2.3).

The radiotherapy doses for each treated site will be recorded. The doses to the

corresponding normal tissues will also be recorded. The maximum dose to each site while staying within dose constraints will be described. The dose to each lesion will also be compared to the local control of the corresponding lesion and described.

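### The only response population in Section 11.1.1 is patients re-evaluated after completing radiotherapy, so treated patients who stop early or are never assessed drop out of the response rate (minor)

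*Combined protocol and SAP*

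**What the plan says.** Section 2.4.1 says that, to describe clinical efficacy, "we will also evaluate objective response rate, treated lesion control, and the patterns of failure". Section 11.1 gives response its rank: "Although response is not the primary endpoint of this trial, patients with measurable disease will be assessed by standard criteria".

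Section 11.1.1 then defines two populations. For toxicity: "All patients will be evaluable for toxicity from the time of their first treatment with radiotherapy". For objective response: "Patients who have had their disease re-evaluated following completion of radiotherapy will be considered evaluable for response", followed by "These patients will have their response classified according to the definitions stated below". The categories in Section 11.1.4.1 are complete response, partial response, progressive disease and stable disease. There is none for early death, withdrawal or a missing scan.

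Section 5.6 lists how a patient can leave the study: intercurrent illness that prevents SBRT, unacceptable adverse events, death, withdrawal, or "General or specific changes in the patient's condition render the patient unacceptable for further treatment in the judgment of the investigator/treating physician".

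Section 12.2 states: "The maximum sample size will be 25 evaluable patients according to the schema above". Section 12.5 says of the secondary endpoints: "The results of analyses will be described but no formal statistical analysis will be performed". Nothing in Section 12 gives another denominator for response or a rule for patients without an assessment.

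**The concern.** Membership of the response population depends on two facts that are known only after treatment starts: radiotherapy was completed, and a later assessment exists. A treated patient who fails either condition is not classified and so cannot enter the rate. Patients who die or deteriorate before a scan are among those who can be lost this way, and under the usual convention they would count as non-responders. Leaving them out raises the reported rate.

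Toxicity and response would also be reported on different groups. A patient with severe early toxicity who is never rescanned counts in the toxicity rate but not in the response rate. A reader who sets the two figures side by side to weigh benefit against harm would not be comparing like with like. With at most 25 patients, each one is worth 4 percentage points, so a few exclusions are visible in the result.

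**Working it through.** **The plan's own figures.** No response rate, or precision for one, is stated. The one design figure is the 78.8% power of the toxicity stopping rule (Section 12.1). An exact binomial recursion with stopping at 2 events by patient 2, 3 by patient 14 and 4 by patient 25 gives 78.84% at a true rate of 20%. It reproduces, and it does not depend on response.

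**Inputs**
- N = 25 (Section 12.2). Because evaluability for toxicity begins at first treatment, these are taken as patients who started SBRT. All are assumed to have measurable disease.
- Response rate among assessed patients: 52%. This is an assumption, taken from the prospective Phase II SBRT study in Section 2.3 (21% complete + 31% partial).
- d, the number of treated patients excluded: not given in the documents. The values 1 to 3 are assumed, with 0 as the reference.

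**Inflation factor.** With r responders among the 25 − d assessed, the evaluable-only rate is r/(25 − d). The all-treated rate, with unassessed patients as non-responders, is r/25. Their ratio is 25/(25 − d).

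**Size.** All-treated rate = 0.52 × (25 − d)/25.

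| d | 25/(25 − d) | Evaluable-only | All-treated | Overstatement (points) |
|---|---|---|---|---|
| 0 | 1.000 | 52.0% | 52.0% | 0 |
| 1 | 1.042 | 52.0% | 49.9% | 2.1 |
| 2 | 1.087 | 52.0% | 47.8% | 4.2 |
| 3 | 1.136 | 52.0% | 45.8% | 6.2 |

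Fixing 13 responders in 25 (52% of all treated) gives a similar picture: 13/24 = 54.2%, 13/23 = 56.5% and 13/22 = 59.1%, against 52.0%, or 2.2, 4.5 and 7.1 points.

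**How many might be lost to death alone.** Section 2.3 reports overall survival of 32 months in the same SBRT study. Read as a median, with exponential survival, the proportion dead by t months is 1 − 2^(−t/32).
- t = 3 (first post-treatment imaging marked in the Section 10 calendar, counted from the first day of SBRT): 1 − 2^(−3/32) = 6.3%. That is 0.063 × 25 = 1.6 patients, and 0.52 × 6.3% = 3.3 points.
- t = 2 (Section 11.1: re-evaluation within one month of completing radiotherapy, which may run to Day 28): 1 − 2^(−2/32) = 4.2%. That is 1.1 patients, and 0.52 × 4.2% = 2.2 points.

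**Direction.** Take d = 3 with 11 responders among 22 assessed (50%). If none of the excluded patients responded, the all-treated rate is 11/25 = 44%. If all three did, it is 14/25 = 56%. The second case is possible only for patients who stopped SBRT early and were scanned anyway, whom the literal wording also excludes. For a patient with no assessment at all, the upward direction follows from the non-responder convention.

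**The case against.** The strongest reply is that little hangs on this rate. Response rate is absent from the objectives in Section 1 and from the endpoint lists in the study summary and Sections 12.1 and 12.5. It appears as a planned measure only in the rationale of Section 2.4.1. No stopping rule, success criterion or sample size uses it. Lesion control and progression-free survival are timed from the start of treatment and estimated by Kaplan-Meier without this evaluability rule. Early deaths are therefore counted in overall survival, and in progression-free survival as the study summary defines it, although Section 11.1.5 omits death. It can also be said that Section 11.1.1 only defines who can be classified and never uses the word denominator. All of this limits importance. It does not supply another population, and a descriptive rate still needs one.

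A reader might infer more than the documents support:
- *That the excluded patients are mostly treatment failures.* Withdrawal, toxicity and intercurrent illness are not tumour non-response. Removal under Section 5.6 also does not by itself mean that no scan exists, since Section 5.5 keeps patients removed for adverse events under follow-up, though it does not promise imaging.
- *That 13% to 29% would die before a 3-month scan.* Those figures follow from the 6 to 15 month median survival in Section 2.1, which describes metastatic renal cell carcinoma in general. This trial selects patients with limited disease, ECOG 0-2 and at least 3 months' life expectancy.
- *That the first scan is necessarily at 3 months.* The Section 10 calendar marks it there, but Section 11.1 asks for earlier re-evaluation, with CT within 28 days of each follow-up visit.
- *That the next trial would be sized on this rate.* Section 2.4 says the data will help with sample size but does not name response.

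**Conclusion.** The concern holds as a minor point. The only response population in the plan is selected on completing SBRT and being assessed afterwards, and no other section restores the treated patients who are left out. Against counting unassessed patients as non-responders, the overstatement is about 2 to 6 points for 1 to 3 exclusions of 25, and nil if no one is excluded. This rests on an assumed 52% rate among those assessed and an assumed d. Deaths alone, on the cited SBRT study's survival and an exponential assumption, suggest 1 to 2 patients.

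The size is small against sampling error: the exact 95% interval for 13 of 25 is 31.3% to 72.2%. Upward bias is likely, not certain, for patients who stop early but are scanned. The documents do not support treating the reported rate as badly wrong, or treating any conclusion of the trial as depending on it.

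**What to change.** In Section 11.1.1, replace the response definition with wording to this effect: the denominator for objective response is all patients with measurable target disease at baseline who receive at least one SBRT fraction; any available post-SBRT assessment is used, whether or not SBRT was completed; patients with no post-SBRT assessment count as non-responders, with the reason listed. Show the evaluable-only rate as a supplement, with the number excluded.

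Separately, the timing of the first post-treatment imaging in Sections 10 and 11.1 must be reconciled, because it sets the window in which patients can be lost unassessed.

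The cost is a few lines of text and a slightly less favourable response rate. The sample size, the toxicity boundaries and the 78.8% power are unchanged.
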